Official Title:	The Use of a Consumer-Based mHealth Dietary App and Health Coaching with Kidney Transplant Recipients Study Information
NCT Number:	NCT05151445
Document Name:	Study Protocol and Statistical analysis Plan
Document Date:	05/05/2021

Study/Project Title: The Use of a Consumer-Based mHealth Dietary App and Health Coaching with Kidney Transplant Recipients

I. Objectives

The purpose of the study is to test the feasibility mHealth dietary app + health coaching for improving primary outcomes (recruitment, retention, and adherence) and secondary outcomes (perceived stress [Perceived Stress Scale], exercise self-efficacy[Exercise Self-efficacy Scale], vegetable intake [Fruit, Vegetables, and Fiber Screen] fat intake [Lose-it Premium database], carbohydrate intake [Lose-it Premium database], weight, blood pressure [Wi-Fi weight scale using the Lose-it Premium database], heart rate [Wi-Fi blood pressure cuff using the Lose-it Premium database], and the minutes of physical activity per day [Lose-it Premium database])

Background and Rationale Weight gain and obesity are common after kidney transplant, often leading to the development of cardiovascular disease, post-transplant diabetes, and death.¹ The increase in weight gain during the first year after transplant is associated with the use of immunosuppressive medications, and changes in lifestyle, such as dietary intake and insufficient physical activity. Moreover, weight gain is affected by factors such as, age, sex, race, and stress.² Evidence indicates that kidney transplant recipients who gain less weight after transplant are physically active, consume fewer carbohydrates, consume more vegetables, and experienced less stress.³ Further, limiting dietary fat and increasing post-kidney energy expenditures aid in preventing early insulin resistance and cardiovascular disease.^{4 5}

However, few studies have tested dietary and physical activity interventions using real-time mobile health applications (mHealth) to enhance lifestyle self-management of care with kidney transplant recipients.⁶

Our proposed study seeks to shift the paradigm for promoting diet intake and physical activity using education and self-report to provide a powerful combination of mHealth dietary app and health coaching (set goals, provide ongoing feedback, and self-monitor behaviors). To our knowledge, this is the first time a mHealth dietary app and health coaching intervention has been used in kidney transplant recipients to link real-time data for monitoring dietary intake and physical activity.

The long-term goal of this work is to enhance well-being in kidney recipients via lifestyle self-management of care for dietary intake and physical activity to ultimately prevent chronic diseases. The proposed study is important because early weight gain after kidney transplant is associated with adverse effects on the transplanted kidney function resulting in increased health care cost and poor quality of life.⁷ Interventions are needed to monitor kidney transplant recipients diet and physical activity in real-time to prevent health decline.

The goal of the proposed feasibility study is to recruit a sample (N = 20) of post-kidney transplant recipients (age 18 and above) who will receive the mHealth dietary app + health coaching intervention for 12 weeks. We will assess changes over time for the primary outcome and secondary outcomes from baseline to 4, 8, and 12 weeks. We plan to submit our findings for publication to the Journal of Progress of Transplantation (Impact factor 0.958) or Trends in Transplantation (Impact factor 0.1.69). We *hypothesize* that the mHealth dietary app + health coaching intervention will improve adherence for recording diet and physical activity, decrease perceived stress, increase exercise self-efficacy, increase vegetable intake, decrease fat intake, decrease carbohydrate intake, improve weight control, improve blood pressure control, improve heart rate and an increase the number of minutes of physical activity per day. We will

also examine biological differences among the secondary outcomes of perceived stress, exercise self-efficacy, vegetable intake, fat intake, carbohydrate intake, weight, blood pressure, heart rate and minutes of physical activity per day, as previous studies have reported differences in outcomes based on age, sex, and race.^{8,9} The rationale for our hypothesis is that progression of cardiovascular disease and chronic disease may be slowed with daily tracking of dietary and physical activity.

II. Procedures

The procedures should include the following:

A. Research Design

A feasibility study will be utilized to establish the recruitment, retention, and adherence with post-kidney transplant recipients using a consumer-based mHealth dietary app + health coaching.

B. Sample

Inclusion Criteria

(a) age 18 or older men and women, (b) functioning KTR (not on dialysis), (c) ability to speak, read, and hear English, (d) possession of a smartphone capable of accessing and downloading a mHealth dietary app (e) Wi-Fi or Internet access, (f) greater than 3 months post-transplant (due to medication adjustments and decreased functional levels), (g) not hospitalized, and (h) capable of self-consent per capacity screening.³²

Exclusion Criteria

(a) Participation in a weight loss program, (b) participation in a structured exercise program, and (c) diagnosis of dementia.

How will subjects be selected?

The participants will be recruited or contacted from a list of kidney recipients that have already requested they be contacted for future studies from our previous study (**IRB Protocol Number: 2017B0084**). This list consists of approximately 60 people. This study will also be advertised at the Ohio State University Medical Center Kidney Transplant monthly support group. Fliers with study information will be made available at the support group. The support group leader will also inform the group participants about the study.

After participants meet the initial screening requirements in the recruitment process, we will determine capacity to obtain verbal consent using the Evaluation to Sign Consent Form (ESC). The ESC consists of five questions (“What are risks associated with the study?” “What are two potential risks for participating in the study?” “What is expected from you in this study?” “What if you do not want to continue the study?” “What if you experience discomfort?”) and takes less than 10 minutes to complete. The ESC allows the participant to reflect upon their understanding of the research protocol by answering the five questions. Participants must answer all five questions correctly to be included in the study. Anybody who is able to answer all five questions correctly will then be read verbal consent script by the study team.

C. Measurement / Instrumentation

Participant **Demographic Information** (10 minutes) will be obtained using a seven-item questionnaire demographics form and **Comorbidity Data** will be gathered using the Charlson Comorbidity Index³³ to describe the patient population. **Aim 1: Recruitment** (percent approached),

will be recorded in REDCap by the RA. **Retention** (percent dropped) will be recorded in REDCap by the RA. **Adherence** (percent to adhere to logging daily dietary intake and physical activity) will be recorded continuously each day by the “Lose-It” app. **Aim 2: Perceived Stress** (10 minutes) will be evaluated by using the Perceived Stress Scale (PSS).³⁵ The PSS is a 10-item questionnaire using a Likert Scale to rate feelings of stress from 0 “never” to 4 “very often.” The PSS has demonstrated excellent test-retest reliability (intraclass correlation coefficient = 0.954) and internal consistency (Cronbach's alpha = 0.810) with adults who have chronic disease.³⁶ **Exercise Self-Efficacy** (10 minutes) will be evaluated by using the Self-Efficacy for Exercise (SEE) Scale. The SEE is a 9-item questionnaire using a Likert Scale to rate feelings of stress from 0 “not confident” to 10 “very confident.” The SEE has demonstrated excellent internal consistency ($\alpha = 0.92$) for adults living with chronic disease.³⁷ **Vegetable intake** will be measured using the Block Fruit-Vegetable-Fiber Screener. The Block Fruit-Vegetable-Fiber Screener (5 minutes) has demonstrated high reliability (Spearman r -value of 0.71).³⁸ This brief screening tool includes seven questions about fruit and vegetable intake and three questions about foods high in fiber, magnesium, and potassium. **Fat Intake and Carbohydrate Intake** (5 minutes) will be recorded each day by the participant using the “Lose-It” app. **Weight** will be measured each day by the participant using a wireless Wi Fi weight scale. The data from the wireless weight scale will sync the data from the participant's mobile phone to the premium password-protect “Lose-It” database each day. **Blood Pressure and Heart Rate** will be recorded each day by the participant using a wireless Wi Fi blood pressure cuff. The data from the wireless cuff will sync from the participant's mobile phone to the premium password-protect “Lose-It” database each day. **Minutes of Physical Activity per Day** will be recorded each day by the participant using the “Lose-It” app. **Clinical Frailty Scale** (5 minutes) will be used to measure the frailty level of each participant. The screening tool has demonstrated high reliability in adults. This brief screening tool consist of nine questions about a person's level of frailty.

D. Detailed study procedures

The “Lose-It” app will be set up with Gmail accounts with unique unidentifiable codes developed by the research team. Participants will be instructed how to download the “Lose-It” app virtually using Zoom. In addition, participants will be taught how to sync to their smartphone and retrieve data from their app. The participants will be trained to enter their dietary intake and physical activity daily for 12-weeks.

Participants will monitor their vegetable intake, fat intake, carbohydrate intake, weight, blood pressure, heart rate and the minutes of physical activity per day using the “Lose-It” app. Wi-Fi connected weight scales and blood pressure cuff will be supplied for weight and blood pressure monitoring. Participants will be taught how to sync the data from the scales and blood pressure cuff to the “Lose-It” app using the Premium database which will Sync all of the data into password protected database for the research team to access. Participants will perform a return demonstration to confirm that they can record their dietary intake daily, physical activity, weight, and blood pressure using the “Lose-It” app. We also review with the participant the “My Plate” method for proper nutrition and the steps to distance conversion chart. Each participant will be given a copy of both via email.

Session	mHealth App + Health Coaching Intervention Setting: Online video- conference call (Zoom)
Baseline Session (Session 1)	The research assistant (RA) will demonstrate proper “Lose-It” app use, set up the smartphone application, and how to enter their dietary intake, physical activity, weight, blood pressure, heart rate and the minutes of physical activity per day using the “Lose-It” app. The RA will demonstrate how to sync the data from the Wi Fi weight scales and blood pressure cuff to the “Lose-It” app.
Time for session: 90 minutes	Participants will perform a return demonstration to confirm that they can access the “Lose-It” app, sync the data from the Wi Fi scales and blood pressure cuff.

Week 1-12 (Sessions 2-13) Time for session: 30 minutes	
Phase 1: The participant will place the goals (dietary and physical activity) into their “Lose-It” app via smartphone for goal attainment.
 
Phase 2: The participant and the RA will review the electronic report generated from the “Lose-It” app for monitoring or assessing progress for dietary intake and physical activity each week from baseline to week 12.
 
Phase 3: The RA will review with the participant each week for 12 weeks how many days they implemented and achieved the solution for their daily goals.
 
Phase 4: Time will be allowed for any questions.

Risk and Benefits

The risks for harm to you for participating in this study are minimal. You may feel uncomfortable about having the research team knowing about your dietary intake or physical activity level. It is not unusual for people with a transplant to occasionally have difficulty with being physically active and controlling their weight. We are trying to help people with these common problems.

If you agree to take part in this study, there may or may not be direct medical benefits to you.

We hope the information learned from this study will in the future benefit other patients with a kidney transplant who are having difficulty becoming physically active and assessing their dietary intake.

E. Internal Validity

In the previous K award²² study, we found that the primary reason for participants not enrolling (65%) into the study was due to the distance of traveling to the research site. Thus, there is a need to deliver the intervention activities in home settings via Zoom. The delivery of our study research activities is timely due to the Coronavirus (COVID-19) and the fact that our population is immunocompromised. Due to the recent pandemic outbreak of the coronavirus (COVID-19) and since our population is immunocompromised. We will promote sustainability for participating in the study by sending weekly text messages to the participants to thank them for their participation in the study. The conduct of this feasibility study will help identify other limitations to consider for future studies in a larger multisite clinical trial. We will collect data regarding the time spent on delivering the intervention so that we can conduct a cost-effective analysis at a later date.

F. Data Analysis

Descriptive statistics will be used to summarize sample characteristics. **Aim 1)** percent approached, percent dropped, and percent to adhere to logging daily dietary and physical activity will be analyzed using means and standard deviations of these variables and analyzed as differences between the baseline and 3-month measurements using the Wilcoxon Signed-Ranked test. **Aim 2)** Perceived Stress Scale, Exercise Self-efficacy Scale, Fruit, Vegetables, and Fiber Screener, fat intake, carbohydrate intake, weight, blood pressure, heart rate, and the minutes of physical activity per day will be analyzed using the differences among baseline, 4, 8, and 12 weeks using repeated measures analysis of variance using the Friedman's Test. Frailty levels will be collected at baseline and 12 weeks and will be analyzed using means and standard deviations of this variables. **Missing Data:** We will carefully record and code various reasons for missing data (e.g., participants forgot to record data into the "Lose-It" app) and examine the pattern of missing data.

III. Bibliography

2. Aksoy N. Weight Gain After Kidney Transplant. *Exp Clin Transplant.* 2016;14(Suppl 3):138-140.

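### Section I promises primary-outcome change at 4, 8 and 12 weeks, but the Aim 1 analysis uses only baseline and 3 months, so no time course of adherence or retention is analysed

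*Combined protocol and SAP*

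**What the plan says.** Section I of the combined protocol and SAP names the "primary outcomes (recruitment, retention, and adherence") and then, under Background and Rationale, sets one schedule for everything: "We will assess changes over time for the primary outcome and secondary outcomes from baseline to 4, 8, and 12 weeks".

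Section II.F (Data Analysis) splits that schedule. Aim 1, which covers the primary outcomes, gets means and standard deviations and is "analyzed as differences between the baseline and 3-month measurements using the Wilcoxon Signed-Ranked test". Aim 2, which covers the secondary outcomes, is analysed as "differences among baseline, 4, 8, and 12 weeks using repeated measures analysis of variance using the Friedman's Test".

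Section II.C says how the primary data arise. Adherence "will be recorded continuously each day by the" Lose-It app. Retention is defined as ("percent dropped) will be recorded in REDCap by the RA", with no time points given. On duration, Section II.D states: "The participants will be trained to enter their dietary intake and physical activity daily for 12-weeks". The session table there has the app report reviewed with the participant weekly up to week 12.

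**The concern.** The two sections disagree on when the primary outcomes are assessed. Section I's schedule is carried into the analysis of the secondary outcomes but not of the primary ones, and no reason is given.

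The study exists to establish recruitment, retention and adherence, and Section II.E says it should inform a larger multisite trial. For that purpose it matters whether daily logging holds up or fades, and when people leave. A single comparison of baseline with the end of the study is not designed to show either. If the analysis follows Section II.F, the report may carry one adherence figure and one dropout figure, although Section I leads the reader to expect results at three follow-up points.

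**Working it through.** The plan gives no figure to reproduce here, so the check is a comparison of texts plus simple arithmetic.

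**1. Occasions, side by side**
- Section I, primary and secondary outcomes: baseline, 4, 8 and 12 weeks = 4 occasions.
- Section II.F, Aim 2: baseline, 4, 8 and 12 weeks = 4 occasions.
- Section II.F, Aim 1: baseline and 3 months = 2 occasions.

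Weeks 4 and 8 are missing from the analysis of the primary outcomes only.

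**2. Are the data there?** Logging lasts 12 × 7 = 84 days, or three blocks of 84/3 = 28 days. With N = 20 (Section I) and nobody leaving, this gives 20 × 28 = 560 person-days per block and 20 × 84 = 1,680 in all. The app records each day, so an adherence time course needs no new collection. For retention, one participant is 1/20 = 5 percentage points. Section II.C does not say whether the date of dropout is stored.

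**3. What one figure can hide.** Take participant A, who logs 100%, 50% and 0% of days in the three blocks, and participant B, who logs 50% throughout.
- Cumulative score: A = (100 + 50 + 0)/3 = 50%; B = 50%. They look identical.
- Score for weeks 9-12 only: A = 0%; B = 50%. They differ, but the course before week 9 is unseen.

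Section II.F does not say which of these the 3-month measurement is.

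**4. Does a change from baseline make sense for these outcomes?** The app is set up and taught in the baseline session, so there is no logging to score at that point. Dropout is zero at baseline by construction. If dropout is coded 0/1 per participant, every non-zero change has the same sign, and the exact two-sided p-value is 2 × 0.5^d for d dropouts: d = 5 gives 0.063 and d = 6 gives 0.031. It reflects only the count of dropouts. Adding weeks 4 and 8 to that test would not help, so the summary should be descriptive.

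**5. Effect of keeping dropouts in the denominator.** A participant who leaves at the end of week 4 adds 84 − 28 = 56 non-logging days. That lowers the highest attainable overall adherence by 56/1,680 = 3.3 percentage points. Leaving at the end of week 8 lowers it by 28/1,680 = 1.7 points.

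**The case against.** The strongest reply is that little is at risk. Logging is captured daily, the app report is reviewed weekly, and Section II.F undertakes to code the reasons for missing data and examine its pattern. In a single-group feasibility study of 20 people, a 4-weekly table could be produced at any time. This stands as far as the adherence data go, but it does not remove the disagreement between the sections. A general look at missing-data patterns is also not a planned summary of adherence or retention over time.

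Three stronger readings are tempting, and the documents do not support them.
- A reader might infer that the time course is lost. It is unanalysed, not uncollected; only the storage of dropout dates is uncertain.
- A reader might infer that the 3-month point is a calendar window running past the end of logging, so that a perfect logger would score 84/91 = 92%. No session or logging is described after week 12, and the plan states no adherence denominator at all. The term is most plausibly shorthand for 12 weeks, which the same paragraph uses for Aim 2 and for frailty.
- A reader might infer that all three primary outcomes need values at weeks 4, 8 and 12. Recruitment, defined as percent approached, has no course after enrolment.

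The 50% example also holds only if adherence is cumulative. It shows what could happen under one reading, not the size of an error in the plan.

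**Conclusion.** The point holds for adherence and retention. Section I commits to weeks 4, 8 and 12 for the primary outcome, Section II.F analyses Aim 1 at two occasions instead of four, and the sections must be reconciled. As written, no time course of either outcome is analysed.

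The consequence is a less informative feasibility result, not a biased one. Its size cannot be given, because the documents contain no expected adherence or dropout rate. The conclusion rests on reading the Aim 1 sentence as the whole planned analysis of the primary outcomes, and on logging starting only after the baseline session. The 3-month wording is a minor matter of harmonisation.

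**What to change.** In Section II.F, for adherence and retention only:
- Report adherence as the percent of days logged in weeks 1-4, 5-8 and 9-12 (28 days each) and overall (84 days). Keep participants who drop out in the denominator, with their remaining days counted as not logged.
- Report the percent retained at weeks 4, 8 and 12, and record the date of dropout in REDCap.
- Present both as descriptive percentages in place of a change from baseline.
- Write 12 weeks instead of 3-month, so that both aims use the same term.

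Leave recruitment as a single figure, and word the schedule sentence in Section I so that it does not apply to recruitment.

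The cost is a change of wording, a small amount of extra tabulation and one date field if it is not already kept. The downside is that adherence will look somewhat lower with dropouts counted, so the denominator should be stated beside the figure.

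### With one treated group, the planned tests can show change over 12 weeks but cannot attribute it to the intervention, and the Aim 1 Wilcoxon test has no pre-intervention adherence value

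*Combined protocol and SAP*

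**What the plan says.** - **Purpose.** Research Design (II.A): "A feasibility study will be utilized to establish the recruitment, retention, and adherence".
- **Design.** Background and Rationale (I) plans to "recruit a sample (N = 20) of post-kidney transplant recipients" "who will receive the mHealth dietary app + health coaching intervention for 12 weeks". No control group or allocation is described. *Single-arm* is my inference; the document does not use the term.
- **Hypotheses.** The same section expects that the "intervention will improve adherence for recording diet and physical activity, decrease perceived stress, increase exercise self-efficacy", then "increase vegetable intake, decrease fat intake, decrease carbohydrate intake, improve weight control, improve blood pressure control, improve heart rate", and finally more minutes of physical activity. The opening of Objectives also speaks of improving the primary outcomes.
- **Adherence.** Measurement / Instrumentation (II.C) defines it as "percent to adhere to logging daily dietary intake and physical activity", recorded by the study app. Detailed study procedures (II.D) has participants download and learn the app at the baseline session: "The participants will be trained to enter their dietary intake and physical activity daily for 12-weeks". No run-in is described.
- **Tests.** Data Analysis (II.F) compares the three Aim 1 percentages between baseline and 3 months with a Wilcoxon signed-rank test. It compares the nine Aim 2 outcomes across baseline, 4, 8 and 12 weeks with Friedman's test.
- **Not stated.** There is no significance level, decision rule or feasibility threshold, and nothing marks the tests as exploratory.

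**The concern.** The purpose in II.A is to establish feasibility. The hypotheses are worded as effects of the intervention, and II.F tests them within one group. A change between visits has several possible sources, some of which the protocol names itself. It links first-year weight gain to immunosuppression and lifestyle. It admits people from just over 3 months after transplant with no upper limit. It places the study in the COVID-19 pandemic. Diet and activity are entered by the participant and reviewed weekly with the research assistant, so reporting habits may also shift.

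At stake is how the results will read. A significant Friedman test set beside a causal hypothesis invites the reader to credit the app and coaching. For adherence, a primary outcome, the analysis as written has nothing to compare against.

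**Working it through.** **1. Count the hypothesised outcomes.** Adherence (1), stress (2), exercise self-efficacy (3), vegetables (4), fat (5), carbohydrate (6), weight (7), blood pressure (8), heart rate (9), activity minutes (10). Outcomes 2 to 10 are the nine sent to Friedman's test.

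**2. Ask which outcomes can have a pre-intervention value (II.C and II.D).**
- Recruitment and retention: one proportion each for the whole study. There is no within-person baseline to pair with a 3-month value.
- Adherence: app logging starts at the baseline session, so nothing precedes it.
- Fat, carbohydrate, activity minutes: logged in the same app, so no pre-intervention period is described.
- Weight, blood pressure, heart rate: a true baseline only if a first reading comes before coaching.
- Stress, self-efficacy, vegetable screener: questionnaires, so a true baseline is possible.

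**3. See what the Wilcoxon test would do.** If adherence before the app were entered as zero, everyone who logged on any day would show a positive difference. With 20 such people the exact two-sided p-value is 2 × 0.5^20 ≈ 0.000002, however poor the logging. If early logging were used instead, the test would address persistence during the intervention, not improvement caused by it.

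**4. Ask what Friedman's test shows.** It ranks each person's four visits and asks whether any visit differs. It is omnibus, so it does not test the stated directions, and it gives no information on cause.

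**5. Illustrate the size.** The plan has no calculation to reproduce. Inputs: n = 20 (Background and Rationale), k = 4 visits (II.F); assumed alpha 0.05, normal and independent visit errors, no intervention effect.
- Visit-error SD is 1/√2, so the baseline-to-week-12 change has SD √(½ + ½) = 1. The visit means are 0, d/3, 2d/3 and d.
- Statistic: Q = 12/[nk(k+1)] × ΣR² − 3n(k+1) = (12/400) × ΣR² − 300, where R is the rank sum at each visit, referred to chi-square on 3 df.
- Rejections in 4,000 simulated trials: 4.8% at d = 0, 14.7% at 0.3, 35.4% at 0.5, 77.1% at 0.8. The Monte Carlo standard error at 0.5 is √(0.354 × 0.646/4000) ≈ 0.8 percentage points, so repeat runs give 35% to 36%.

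**6. False positives with no drift.** Nine independent tests: 1 − 0.95^9 = 1 − 0.630 = 37.0%. With equal correlation of 0.3 to 0.5 between outcomes (assumed), this falls to about 33% to 27%.

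**7. What estimation would give.** Exact 95% intervals at n = 20 for illustrative counts: 16/20 = 80% (56% to 94%); 18/20 = 90% (68% to 99%).

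**The case against.** The strongest reply is that this is openly a feasibility study. II.E presents it as a way to find limitations before a larger multisite trial, and the Background also says, descriptively, that change over time will be assessed. II.B narrows some rival explanations by requiring more than 3 months since transplant and excluding people in weight-loss or structured exercise programmes. These points stand as mitigation. They reduce the confounding without removing it, and they do not alter the causal hypotheses or the missing exploratory label.

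Several stronger readings are tempting, and the documents do not support them:
- *Twenty people is the problem.* The missing comparator blocks attribution. A larger one-group study would share the defect.
- *Adherence cannot be analysed.* Logging is recorded daily, so its level and its early-to-late course are measurable. Only a pre-app value is missing.
- *Any significant change will be taken as proof of benefit.* The hypotheses are directional, so a change the wrong way confirms nothing, and the plan states no decision rule.
- *The results will set the effect size for the next trial.* No section says so.
- *The error rates are higher.* Paired t-test rates at n = 20 are 24.7% and 56.5% for drifts of 0.3 and 0.5 SD, but the plan uses Friedman's test for these outcomes. Ten tests would give 40.1%, but the tenth is adherence, which has no valid baseline comparison.

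**Conclusion.** The point holds in two parts, and both rest on the text alone. First, the hypotheses attribute change to the intervention while the design and tests can only describe change. Second, the Aim 1 Wilcoxon test is wrong as written: adherence has no pre-intervention value, and recruitment and retention have no within-person baseline.

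The figures are illustrative: about 15% and 35% rejection for drifts of 0.3 and 0.5 SD, and 37% for at least one false positive among nine independent tests. They depend on an alpha of 0.05, on the chosen drift sizes and on independent errors, none of which the documents state. The conclusion does not depend on them. The feasibility data keep their value, and within-person change is worth reporting where a true baseline exists. No control arm is needed, only conclusions that match the design.

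**What to change.** **Data Analysis (II.F), Aim 1.** Drop the Wilcoxon test. Report recruitment and retention as proportions with exact 95% intervals, stating each denominator. Report adherence as a level: each participant's percentage of the 84 days (12 × 7) logged, summarised with a 95% interval and, optionally, described by 4-week period. Define a logged day and say how days after drop-out count.

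**Data Analysis (II.F), Aim 2.** Make estimated within-person change with 95% intervals the reported result, and label the Friedman tests exploratory. Friedman's test yields no interval, so name the estimator. For app-logged fat, carbohydrate and activity minutes, define the first logging week as the reference and call it an on-intervention value.

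**Objectives and Background (I).** Remove *improving* as applied to the primary outcomes and *improve adherence* as a hypothesis. For the secondary outcomes, suggested wording: *We will estimate within-person change at 4, 8 and 12 weeks, with 95% confidence intervals, to inform a controlled trial. Change will not be attributed to the intervention.*

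**Cost.** No new participants, visits or data. There is a small amount of added analysis, and the study gives up efficacy claims that its design cannot support.

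### No acceptable level is set for retention or adherence, the recruitment goal has no denominator or period, and the Aim 1 Wilcoxon test cannot show whether any of the three rates is good enough

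*Combined protocol and SAP*

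**What the plan says.** Section I (Objectives) opens: "The purpose of the study is to test the feasibility mHealth dietary app + health coaching for improving primary outcomes", and names recruitment, retention and adherence as those outcomes. Section II.A (Research Design) repeats the aim: "A feasibility study will be utilized to establish the recruitment, retention, and adherence".

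Section II.C (Measurement / Instrumentation) names one measure for each. Recruitment is "percent approached", retention is the percentage dropped, and adherence is the percentage logging diet and physical activity daily in the app. None has a target, and no number of logged days is said to make a participant adherent.

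Two figures bear on recruitment. Background and Rationale sets a goal of N = 20. Section II.B (Sample) says of the contact list: "This list consists of approximately 60 people". The same section adds a second source of unstated size, the monthly support group. No recruitment period is given.

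Section II.F (Data Analysis) summarises the three Aim 1 percentages by means and standard deviations, and has them "analyzed as differences between the baseline and 3-month measurements using the Wilcoxon Signed-Ranked test". It states no alpha, no sidedness and no confidence intervals. On later use, Section II.E (Internal Validity) says: "The conduct of this feasibility study will help identify other limitations to consider for future studies in a larger multisite clinical trial".

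**The concern.** A question of the form *is this feasible?* needs two things: an estimate of each rate, and a prior statement of what rate would be acceptable. For retention and adherence the plan supplies the first only in part (means and standard deviations, no intervals) and the second not at all.

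The signed-rank test does not fill the gap. It asks whether paired values within a person have shifted. It does not ask whether a completion or logging rate is high enough to carry into a larger study.

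The missing bar cannot be supplied fairly at analysis. By then the percentages are known, and with 20 participants the intervals are wide enough that a bar chosen afterwards could support either conclusion. What is at stake is the standing of the primary conclusion. The data themselves remain usable.

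**Working it through.** **Inputs from the document.** N = 20, single group (Background and Rationale). Follow-up of 12 weeks, so 12 × 7 = 84 logging days. Contact list of about 60 plus an uncounted support group (II.B). Wilcoxon signed-rank test, baseline against 3 months (II.F). N = 20 comes with no alpha, power, effect size, precision or dropout assumption, so there is no calculation to reproduce.

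**Step 1. What the planned test answers for each outcome.**

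- *Recruitment.* A person is recruited or not. There is no within-person baseline and 3-month pair, so the test is undefined.
- *Retention.* Everyone is present at baseline. If retention is forced into the test (1 at baseline, 0 at 3 months for a dropout), only the k dropouts give non-zero differences, all of one sign. The exact two-sided p is then 2 × 0.5^k. For k = 5 this is 0.0625, and for k = 6 it is 0.031. A small p would signal loss of participants, not feasibility.
- *Adherence.* The app is first taught at the baseline session (II.D), so logging before it is plausibly zero; this is an assumption. Suppose the 20 participants log 1%, 2%, ..., 20% of days at month 3 (mean 10.5%). All 20 differences share a sign, so p = 2 × 0.5^20 = 0.0000019. If baseline instead means an early, high level of logging and participants fall by 1, 2, ..., 20 points, p is again 0.0000019. If adherence is high and steady, with changes of 1 to 20 points alternating in sign, p = 0.87.

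So the same p-value can go with very poor logging or with good logging that is slipping, and steady good logging gives a large p.

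**Step 2. How precisely 20 participants measure a proportion.** Exact (Clopper-Pearson) 95% limits for x of n: the lower limit is the 0.025 quantile of Beta(x, n − x + 1), and the upper limit is the 0.975 quantile of Beta(x + 1, n − x).

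| Retained | Estimate | 95% CI |
|---|---|---|
| 14/20 | 70% | 45.7-88.1% |
| 16/20 | 80% | 56.3-94.3% |
| 18/20 | 90% | 68.3-98.8% |

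The three intervals overlap heavily. All of them contain 70% and 80%, for example.

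**Step 3. What a pre-set rule would do.** The threshold here is an illustration, not a figure from the document. For the rule of at least 16 of 20 retained, the pass probability is the sum over x = 16 to 20 of C(20, x) p^x (1 − p)^(20 − x).

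| True retention | P(pass) |
|---|---|
| 90% | 0.957 |
| 80% | 0.630 |
| 70% | 0.238 |
| 60% | 0.051 |

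Without a rule, the probability of declaring retention feasible is undefined at every true rate.

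**The case against.** **Small feasibility studies may be purely descriptive.** This is the strongest point on the other side. Section II.A can be read as estimation, and Section II.E speaks of finding limitations to consider in later work, not of a formal gate to the next trial. How elaborate the progression rule should be is partly a design preference. What remains is that Section I sets out to test feasibility, and that Section II.F attaches a test to Aim 1 that cannot address it. Even a purely descriptive plan would report intervals and leave the test out.

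**A reader might infer that the p-value is the plan's decision tool.** The document does not support that. Means and standard deviations are listed first, no alpha is set, and no p-value is tied to a feasibility conclusion. The Wilcoxon test is the only inferential analysis for Aim 1; there is no decision rule.

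**A reader might infer that any result could be called feasible.** That goes too far. Enrolling fewer than 20 would miss a stated goal, and there is a directional hypothesis that adherence will improve. But the goal has no period or denominator, the hypothesis has no amount, and neither sets an acceptable level of retention or adherence.

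**A reader might infer a planned enrolment rate of 20/60 = 33%.** The document does not imply it. The support group is a second source, and enrolment could reach 20 before everyone on the list is contacted.

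**Conclusion.** The point holds for retention and adherence, where no acceptable level is stated. For recruitment it holds in a narrower form: there is a goal of 20, but no denominator or period by which to judge the rate. The planned Wilcoxon test cannot supply the missing judgement for any of the three, so a conclusion that retention or adherence was feasible would be post hoc.

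The size of the problem is set by the precision at N = 20, where an interval such as 56.3-94.3% around 80% leaves ample room to choose a bar afterwards. The adherence p-values rest on assumed data patterns, one of which takes logging before the app as zero. The pass probabilities rest on an illustrative threshold and on participants dropping out independently. The main conclusion needs none of these assumptions, because it follows from what Sections II.C and II.F contain. The change should be made before enrolment.

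**What to change.** In Section II.F, drop the Wilcoxon test for Aim 1 and report:

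- **Recruitment:** number enrolled divided by number approached, across the contact list and the support group together, with an exact 95% CI, over a stated recruitment period. Define what counts as approached for people reached by flier or announcement.
- **Retention:** proportion of enrolled participants completing week 12, with an exact 95% CI.
- **Adherence:** percentage of the 84 days logged by each participant, with days after dropout counted as not logged, averaged over participants and given a bootstrap 95% CI. State whether a logged day needs diet, activity or both.

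In Section II.A, before enrolment, state a progression threshold for each outcome and how the three combine into one conclusion. The levels are for the sponsor to choose; the 16/20 rule above only shows how a candidate can be examined. Express the retention rule so that it still applies if fewer than 20 enrol.

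The cost is about a paragraph across the two sections, with no extra participants or visits; the only added record is who was approached, by source. The downside is that the study can then fail its own criterion. At N = 20 such a rule also discriminates only moderately: the illustrative one passes 63% of the time at true retention of 80% and 24% at 70%. The text should acknowledge this.
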